**4.4 Secondary Subjects**

N/A

**4.5 Number of Subjects**

**A. Total Number of Subjects**

We anticipate 30 total subjects to enroll in this pilot study.

**B. Total Number of Subjects If Multicenter Study**

N/A

## 4.6 Consent Procedures

### A. Consent

#### ▪ Documenting Consent

The subject's parent will be asked to provide oral consent over the phone during the primary screening process to obtain confidential information related to eligibility and orientation scheduling. The parent will be read a statement of confidentiality (See Screening Script). A list of the items that will be covered in the screening interview will be read to the parent to ensure that the parent is aware of the screening process and the questions that are going to be asked of them. Study staff will ask the parent if they have questions or concerns prior to asking for oral permission and proceeding with screening-related questions. The study staff will ask the parent for permission to document identifiable information related to the subject's eligibility in the study. Verbal consent to the screening protocol will be documented on the Screening Script. The person obtaining oral consent will also sign and date this form. Initial eligibility will be determined using this screening tool and minimizes subject burden to the study location for the secondary screening and orientation. The phone screening script includes self-reported information including age, approximate weight and height of the child, availability to complete the study and current sleeping patterns.

Eligible individuals will be invited to the sleep center for an orientation. A secondary screening process will be needed to determine further eligibility (See Orientation Eligibility Form). We anticipate that a secondary screening process prior to the full written informed consent/assent process will minimize subject burden. Oral consent and assent from both the parent and child will be documented on a secondary screening document by the research coordinator/research assistant(s) to carry out procedures for additional checks for eligibility (measured BMI, typical sleep and availability to complete the study, complete the SDI-S questionnaire). These procedures are outlined in the Orientation Eligibility Form, which will be used to inform the parent and child about the orientation screening procedures. Study staff will ensure that the parent and child do not have any follow up questions or concerns. After oral consent and assent is obtained from both the parent and child, the research staff member who delivered this information will sign and date the form.

Following the additional screening procedures highlighted above, eligibility will be determined by the study staff based on inclusion/exclusion criteria. Eligible subjects will be asked to complete the written Parental Informed Consent Document and Assent for Participation in Research Activities Document before further research procedures can take place (See Consent section for further details on consent/assent process). A parental informed consent document will be used to obtain consent from the parent of the participant. Additionally, because we are recruiting children, every child will be asked to provide assent and will sign the assent document to declare assent to research study procedures.

#### Document List:

- a. Parental Informed Consent Document
- b. Assent for Participation in Research Activities Document

On the consent form, we ask parents to indicate if they are willing to be contacted in future research studies. If a parent initials 'Yes, I agree to be contacted about future research studies,' we will provide them with a Contact Form which will include the name of parent, the name of the participant, the date as well as the preferred contact method. Parents and participants will be informed that in the event there is another research study they can participate in, the study staff will contact the family using the information provided on the Contact Form. The

Contact Form is the only document used to revisit families that documented interest in participation in additional research studies at Rutgers Sleep Lab.

▪ **Waiver of Documentation Of Consent**

N/A

▪ **Waiver or Alteration of Consent Process**

N/A

6.

7. **Consent Process**

▪ **Location of Consent Process**

The consent process will take place in Loree Classroom Building in a closed-door office space.

▪ **Roles for Individuals Involved in Consent**

The study coordinator will be responsible for obtaining written consent/assent at the initial orientation visit from both the parent and the child.

▪ **Coercion or Undue Influence**

The consent process is anticipated to take approximately 10-20 minutes, or as long as the participant needs to make an informed decision about participation in the study. All individuals involved in the informed consent/assent process will be educated that their participation in the research study is completely voluntary. Participants will be reminded that they have the ability to withdraw at any time and that their decision to participate will not have any impact on their availability of care. All study-related information will be clearly communicated and in writing in an organized fashion with understandable language. Exculpatory language will not be used in written consent or discussions about research.

**4.7 Special Consent/Populations**

A. **Minors-Subjects Who Are Not yet Adults**

▪ **Criteria for Consent of Minors**

Parents will be asked to report the age of their child prior to study enrollment. This research study will focus on adolescents (14-17 y), and therefore, we expect a parent to be available and present at all study meetings.

a. **Wards of the State**

N/A

b. **Research in NJ Involving Minors**

This research involving children will pose no more than minimal risk to the participants. Permission of one parent is sufficient even if the other parent is alive, known, competent, reasonably available, and share legal responsibility for the care and custody of the child. Assent to research procedures will be obtained from all children. The investigators will obtain assent on the Assent for Participation in Research Activities Form. The child will print, sign and date the assent form. Parental consent will be obtained using the Parental Informed Consent Form. The name of the child will be printed on the form, and the parent will print, sign and date the form. The person obtaining consent will sign and date both the parental consent and assent forms before enrollment can occur.

**c. Research Outside of NJ Involving Minors**

N/A

▪ **Parental/Guardian Permission**

Participants in our study will be between the ages of 14-17 years. Therefore, parental permission to participate in the research study will be required.

▪ **Assent Process**

During the orientation, trained study staff will go through the consent document with the parent. The parent will have the opportunity to ask questions about the study. Next, the staff member will review the assent form with the child to ensure that the child has a clear understanding of the study procedures. Research staff members will ask the child if they have any questions or concerns related to the study protocol. The study staff will remain engaged with both the child and the parent during the entire duration of the consent/assent process. Following review of the consent and assent documents, the parent and child will have the opportunity to discuss the study. After the decision is made, and the study staff ensures that all questions and concerns have been addressed, the parent will be asked to sign the consent document and the child will be asked to sign the assent document. We will obtain assent for all children who have parent consent to research participation. Individuals will be asked about any questions or concerns they may have prior to assent and also be made aware that their participation is completely voluntary.

**a. Documentation of Assent**

Trained study staff will review the assent form with the child while the parent is present. Assent will be considered documented after the child prints, signs and dates the Assent for Participation in Research Activities Form.

**B. Non-English Speaking Subjects**

N/A

**C. Economic Burden and/or Compensation for Subjects**

▪ **Expenses**

The only expense that participants are anticipated to accrue as a direct result of participation in this study is the cost of travel to the sleep center.

▪ **Compensation/Incentives**

At the end of the follow-up visit, when devices have been returned, participants will be compensated (\$10/day = maximum \$70 for their participation in the study according to protocol adherence (payments will be made in the form of a giftcard).

▪ **Compensation Documentation**

Participants who adhere to the protocol guidelines described at the orientation will receive a receipt of the payment and study staff will make copies of these receipts. Receipts will be stored in a locked filing cabinet in a locked office.

**D. Risks and Benefits to Subjects**

▪ **Description of Subject Risk**

The sleep study procedures pose minimal risk to participants. Participants will be asked to wear sleep monitoring and physical activity devices, and there is a rare risk (estimated at 1 out of 100 persons) that the devices may cause irritation to the skin or be slightly uncomfortable to wear.

Participants may experience travel inconvenience, as they are asked to travel to the study center for orientation and the follow-up visit. We will ask participants to complete sleep diaries and complete daily call-ins to report sleep patterns, which may serve as a small inconvenience to participant participation. Half of participants will be asked to increase their sleep to 10 h/night. A change in sleep patterns, bedtime routine or wake routine may be an emotionally charged or negative psychological experience for the subject and/or their families.

Participants will be asked to complete a sleep disorder questionnaire upon study enrollment to determine if they have a sleep disorder that would hinder their ability to participate any further in the research study. Therefore, there is a risk that the participant may endure psychological stress as a result of completion of this assessment.

There is a rare risk that confidentiality of the subjects and/or their families may be broken. However, the study staff will be trained to minimize these risks to ensure confidentiality is not broken before, during and after data collection.

**▪ Risks to Non-Subjects**

The subject's parent(s) will need to be engaged in the research study in order to ensure that the child is following the study protocol. Changes in behavior that may be attributed to study protocol procedures may be a psychological risk to non-subjects, as the study protocol may disrupt daily activities. Additionally, parents are expected and will be required to travel to the study center their child, and therefore, they may experience a travel inconvenience for their time.

**▪ Minimizing Risks**

In order to minimize risk, the research team will be composed of members who have sufficient expertise and experience to conduct the research. Actigraph and accelerometer data will be collected using standard procedures. The study staff will be trained in device placement to ensure that the participant is comfortable before leaving the sleep center. An unknown preexisting condition that is discovered at the research lab will prompt the study staff to explain to the participant that they need a clinical examination to determine their condition and that no medical diagnosis has been made. Additionally, study staff will have resources available to subjects in the event that they ask for further medical advising related to the condition. Data confidentiality will be protected by storing all data on a secure server recommended by Rutgers IT department on a password protected computer. All hard copies of participant data will be stored in a locked filing cabinet in a locked office space.

**▪ Certificate of Confidentiality (CoC)**

N/A (will not be obtained; not funded by NIH)

**▪ Potential Benefits to Subjects**

At the follow-up study visit, trained study staff will have the capacity to share individualized sleep reports with the study participants and their families. These sleep reports may be a valuable tool for participants to learn about their own sleep habits. Educational materials will also be distributed to the parents to help the adolescent improve sleep. Additionally, participants will be compensated according to study protocol adherence. Adherence will result in a maximum compensation of \$70.

**▪ Provisions to Protect the Privacy Interests of Subjects**

The study coordinator will be responsible for coordinating all aspects of research that involve confidential information, including participant scheduling, orientation, participant call-ins and follow up visit to ensure subject

privacy is protected. Participants will be instructed to contact the study coordinator with any questions or concerns related to the study protocol, which will limit the number of investigators that may be aware of the participant's and his/her parent's identity.

**▪ Research Team Access to Subject Data**

The study coordinator and PI will have access to a password-protected folder on a shared drive which will contain the data collected from the study.

**4.8 Secondary Data**

N/A

**A. Chart/Record Review Selection**

N/A

**B. Secondary Specimen Collection**

N/A

**▪ Specimen Storable Procedures**

N/A

**▪ Specimen Data**

N/A

**5.0 Special Considerations**

**5.1 Health Insurance Portability and Accountability Act (HIPAA)**

N/A

**5.2 Family Educational Rights and Privacy Act (FERPA)**

N/A

**5.3 NJ Access to Medical Research Act**

N/A

**5.4 Code of Federal Regulations Title 45 Part 46 (Vulnerable Populations)**

**A. "Special" Classes Of Subjects**

- Children in our study are defined as persons who have not attained the legal age for consent to procedures involved in the research. We plan to seek child assent, or a child's affirmative agreement to participate in research. Permission will be obtained via parental consent to allow their child's participation in the research. Parent is defined as a child's biological or adoptive parent. The study coordinator, trained in informed consent procedures, will obtain written informed consent for the parent of the child and written assent from the child before proceeding with study. We anticipate that the study procedures will present no more than minimal risk to the subjects who participate in the research.

**6.0 Research Data Protection and Reporting**

**6.1 Data Management and Confidentiality**

A. As this is a pilot study, primarily descriptive statistics will be conducted on sleep and physical activity data. No formal analyses will be conducted on feasibility/acceptability questionnaire and subsequent interview responses. Mixed-model ANOVAs will compare changes in sleep and physical activity between both groups.

- B.** All data will be de-identified (a subject id number will be assigned to each participant and used to track each data file) and will be stored on a password-protected shared drive folder (the study coordinator and PI will be the only two with access to this folder).
- C.** All sleep and physical data will be separately independently by the study coordinator and PI to determine reliability in the application of scoring rules. Questionnaire data will be entered by two study staff members independently and then compared to ensure accuracy.
- D.** Sleep and physical activity data will be obtained from an output that the device software provide. This data will be checked against sleep diary and call-in data and adjusted as necessary by trained study staff. Questionnaire, sleep diary, sleep device and physical activity device data will be aggregated and entered in to a database in SPSS. This file will be stored on a password-protected shared drive folder. The study coordinator and PI will have access to this folder. The study coordinator is primarily responsible for receipt of the data and the PI will ensure its storage. The data will be stored for five years.

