#### B. Research Question(s)

Aim 1: Determine the additional amount of sleep short-sleeping-adolescents (~7h TIB/night) will obtain when asked to increase time-in-bed to 10h/night for seven consecutive nights compared to those who are not asked to increase time-in-bed.

Aim 2: Determine if adolescents are able to comply with study demands: wearing two devices (one on wrist and one on hip) and completing daily sleep diaries and call-ins for seven days.

Aim 3: Acquire participant feedback regarding feasibility and acceptability of increasing TIB for sleep to 10h/night using a questionnaire and semi-structured interview.

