Handouts (See Sleep Health Education Information Sheet) on sleep hygiene practices (i.e., strategies to ensure a good night's sleep) will be reviewed and provided to families. These include a list of caffeinated foods/beverages to avoid after 2pm, not watching TV, using computer/smartphone/tablet or play video games as part of the bedtime routine, and ensuring that the adolescent has a quiet, cool, and dark sleep environment. Research staff will discuss potential barriers to following the protocol and provide strategies to overcome these barriers (e.g., providing participants with an eye mask to block out excess light, discussing the use of fans or white noise machines to decrease noise, turning phone/tablets off or giving these devices to parents when it is time for bed and recording TV shows that begin late at night).

Subjects who are randomized to the control condition will be asked to maintain their typical bedtime and wake times. These subjects will be instructed to wear wrist actigraphs, waist accelerometers, complete sleep diaries and call-ins for 7 days. Handouts and resources on sleep hygiene practices will be reviewed at the end of the study.

Study staff will conclude the orientation session by answering any remaining questions that the family has and scheduling the follow-up visit.

**Week-long study protocol:** Participants are instructed to wear the sleep monitor (on wrist) 24h a day for the entire 7 day period and to wear the physical activity monitor (on hip) during all waking hours for the entire 7 day period. Participants will be given a 7-day sleep diary to complete daily. This provides an additional monitor of sleep which assists in analysis of wrist actigraph data and serves as an effective behavioral strategy to increase adherence to the protocol via self-monitoring. Participants will also be asked to call in twice daily (just prior to bedtime and upon waking in the morning) to a time-stamped voice mail box or send a text to the study's Google voice account. If a family fails to call in/text or calls in bed bed/wake times are outside prescribed times, research staff will follow-up with families by phone to ensure protocol adherence. Research staff will also maintain a rolling calculation of adherence to the sleep schedule for subjects asked to complete 10h TIB.

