**4.3 Subject Randomization**

Condition assignments will be created by the PI and placed in sealed envelopes. Envelopes will be opened during the orientation visit by the study coordinator (there will be n=15 control and n=15 increase to 10h time-in-bed).

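### The planned mixed-model ANOVA of 'changes' has no device baseline and, if run conventionally over seven nights, would drop every participant with a single missing night

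*Protocol*

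**What the plan says.** Section 6.1 A calls the analysis mainly descriptive ("primarily descriptive statistics will be conducted on sleep and physical activity data") and then names one comparative method: "Mixed-model ANOVAs will compare changes in sleep and physical activity between both groups". Section 6.1 D says that questionnaire, diary, "sleep device and physical activity device data will be aggregated and entered in to a database in SPSS".

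The device period is one week. Under section 1.3, "Participants are instructed to wear the sleep monitor (on wrist) 24h a day for the entire 7 day period", and the hip monitor is worn during waking hours over the same days. The devices are handed out at orientation. Section 4.3 has the allocation envelopes opened at that same visit ("there will be n=15 control and n=15 increase to 10h time-in-bed"). No recording before allocation is described.

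Aim 1 in section 1.1 B concerns the extra sleep obtained by adolescents asked to "increase time-in-bed to 10h/night for seven consecutive nights", compared with those not asked. Section 1.6 B makes the actigraph sleep period the primary sleep variable and daily wear time the primary physical activity variable. For the hip device it refers to standard rules on valid days and non-wear. It states no corresponding rule for nights. Section 1.8 A expects staff to go through off-wrist periods and times when the hip device was removed.

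**The concern.** Two things do not fit together. The comparison is of changes, but each device yields only one week of data, all of it after allocation. For physical activity there is no earlier measurement to change from. For sleep there is only the reported typical duration from screening, which is not an actigraph measurement. The repeated dimension that the devices do provide is the night or day.

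In its usual sense, a mixed-model ANOVA is a between-within repeated-measures ANOVA, with arm between and the repeated factor within participants. In that form a participant missing one level of the repeated factor is removed entirely. With seven levels, one unrecorded night discards up to six good ones.

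Aim 2 asks whether adolescents can comply with the device and diary demands, so those removed could be the participants of most interest. The Aim 1 estimate is also meant to inform a later, larger study.

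**Working it through.** **Inputs from the protocol.** Total sample 30 (section 4.5 A: "We anticipate 30 total subjects to enroll in this pilot study"), 15 per arm (section 4.3), 7 nights each (section 1.1 B). Participant-nights: 30 × 7 = 210. Section 1.5 states that no power analysis was done, and no dropout or missing-night rate is given, so there is no planned figure to reproduce.

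**Assumed.** The share p of nights missing, from 2% to 10%.

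**Step 1: participants lost, independent nights.** A participant is complete with probability (1 − p)^7, so the expected number lost is 30 × [1 − (1 − p)^7].

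| p | Missed nights (210p) | (1 − p)^7 | Lost of 30 | Kept |
|---|---|---|---|---|
| 2% | 4.2 | 0.868 | 4.0 | 26.0 |
| 3% | 6.3 | 0.808 | 5.8 | 24.2 |
| 5% | 10.5 | 0.698 | 9.0 | 21.0 |
| 10% | 21.0 | 0.478 | 15.7 | 14.3 |

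**Step 2: what a loss of a third or a half requires.** Solving 1 − (1 − p)^7 = 1/3 gives p = 5.6%, or about 12 of 210 nights. For 1/2, p = 9.4%, or about 20 nights. With k missed nights placed at random among the 210, the expected number of participants affected is 30 × [1 − C(203, k)/C(210, k)]: 2.9 for k = 3, 4.7 for k = 5 and 6.4 for k = 7.

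**Step 3: clustering within persons.** With a beta-binomial model and within-person correlation ρ, P(complete) = B(a, b + 7)/B(a, b), where a = ps, b = (1 − p)s and s = (1 − ρ)/ρ.
- p = 5%: 24% lost (7.2 of 30) at ρ = 0.1, falling to 12% (3.7) at ρ = 0.5.
- p = 10%: 43% lost (12.9) at ρ = 0.1, falling to 24% (7.0) at ρ = 0.5.

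**Step 4: precision.** Assume a between-person SD of 0.7 h and a night-to-night SD of 1.0 h; neither is in the protocol. A seven-night mean has variance 0.49 + 1/7 = 0.633.
- All 15 per arm: SE of the arm difference = √(2 × 0.633/15) = 0.29 h. Simulation with the 5% of nights removed but everyone kept also gives 0.29 h.
- Complete cases at 5% (10.5 per arm): √(2 × 0.633/10.5) = 0.35 h.
- Complete cases at 10% (about 7.15 per arm): √(2 × 0.633/7.15) = 0.42 h. Simulation gives 0.43 h, slightly more because the number kept varies.

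**Step 5: selection.** Suppose shorter sleepers miss more nights: logit(missing) = −2.6 − 1.0 per hour of the participant's mean, between-person SD 0.9 h, about 9% of nights missing, all assumed. The complete-case mean in one arm is then 8.86 h against a true 8.50 h. With the same mechanism in both arms, relative to each arm's own mean, both means rise by about 0.35 h and the arm difference stays at 2.00 h against a true 2.00 h.

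**The case against.** The strongest reply is that the protocol does not commit to this analysis. It names neither the night factor nor a repeated-measures procedure, and it does not say that participants with a missed night are excluded. SPSS appears as the database ("aggregated and entered in to a database in SPSS") and can also fit a likelihood-based mixed model. The word 'changes' might mean typical sleep against the study week, or the factor might be school against weekend nights. If device data are averaged per person before entry, one missed night deletes nobody. The within factor, procedure and missing-data rules are commonly left to an SAP, which is not shown. The protocol also limits missing data through twice-daily contact, staff follow-up and payment per adherent day, and the team reports very high adherence with that payment.

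Much of this stands. The loss is conditional, and the missing rates are assumptions. Three points remain. The method itself is stated, not left open. A typical-sleep baseline would set reported duration against actigraphy and has no counterpart for physical activity. In section 6.1 D, the aggregation reads as bringing several data sources into one file and does not clearly mean averaging per person.

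A reader might infer three stronger claims that the document does not support:
- **That the plan keeps only complete participants.** Nothing in section 6.1 says so.
- **That a few missed nights would cost a third to half of the sample.** Steps 2 and 3 show that this takes about 12 to 20 nights spread across participants.
- **That the Aim 1 difference would be biased upward.** Step 5 shows that missingness common to both arms shifts both means and can leave the difference intact. Missed call-ins are not missed actigraphy, and off-wrist periods may be short.

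**Conclusion.** The point holds in conditional form. The stated comparison of changes has no device baseline, and the named method in its conventional form handles the available data poorly. If seven nights are the within factor with listwise deletion, about 4 to 6 of 30 participants are lost at 2% to 3% missing nights and about 9 to 16 at 5% to 10%. These figures assume independent nights and are smaller under clustering. Under the assumed SDs, the SE of the arm difference rises from 0.29 h to 0.35 h at 5% and to 0.42–0.43 h at 10%.

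Selection towards more compliant participants is plausible but not documented. Bias in the arm difference would need missingness that differs by arm, which the document does not show. Because the analysis is mainly descriptive, this is a modest weakness in a stated method, but one that costs nothing to correct.

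**What to change.** Replace the ANOVA sentence in section 6.1 A with a linear mixed model fitted by REML (SPSS MIXED):
- **Outcome:** nightly actigraph sleep period, using all recorded nights.
- **Fixed effects:** arm, night type (school or non-school) and typical school-night sleep from screening.
- **Random effect:** participant intercept.
- **Report:** the arm difference with a 95% CI, in place of a test of change.

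Use the same form for daily wear time. A day of short wear is an observed low value of that outcome and should stay in.

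A missed night then removes only that night, and every participant with at least one recorded night contributes. The model relies on nights being missing at random given the recorded nights and covariates, so the number of recorded nights should be shown by arm.

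The cost is a change of analysis wording. Typical sleep is already collected at screening, night type follows from the calendar, and no new data, visits or software are needed.
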